1. ABSTRACT

More than one-third of U.S. adults are obese¹. The increasing prevalence of obesity in the U.S. has been accompanied by an increasing prevalence in its associated comorbid conditions including hypertension, diabetes, dyslipidemia, coronary heart disease, stroke, sleep apnea, osteoarthritis, gallbladder disease, GERD, nonalcoholic fatty liver disease (NAFLD/NASH), and cancer. Obesity is associated with an increased risk of all-cause and cardiovascular mortality and accounts for about 2.5 million preventable deaths annually²⁻⁴. Patients with mild to moderate obesity (BMI 30-40 kg/m²), who do not qualify for bariatric surgery are left without an effective management approach to their disease; considering the modest effects seen with medications or lifestyle intervention alone and their ability to achieve >10% total body weight loss (TBWL) only in the minority of patients. Therefore, there is ***significant management gap*** for patients with mild to moderate obesity (BMI between 30-40 kg/m²). **Endoscopic sleeve gastroplasty (ESG) is an endoscopic, minimally invasive intervention that is well positioned to fill the obesity management gap** since it results in more than 10% TBWL in the majority of patients, has excellent safety profile, and is roughly one quarter the cost of bariatric surgery. Clinical data from both the United States (US) and outside the US (OUS) demonstrates a 19.8% TBWL at 18 months after ESG with excellent safety profile. ESG is performed using an FDA approved and commercially available endoscopic suturing device. Despite the excellent clinical experience with ESG, no randomized clinical trials have been performed to evaluate the long-term efficacy of the technique over life-style intervention in producing significant long-term weight loss and improving obesity associated co-morbidities. Level 1 evidence is needed to further advance this promising technique and inform global adaptation. Therefore, we are proposing a randomized controlled trial to evaluate the long-term safety and efficacy of ESG in meeting efficacy endpoints set forth in a consensus statement by relevant societies (American Society of Gastrointestinal Endoscopy [ASGE] and American Society of Metabolic and Bariatric Surgery [ASMBS]) and its impact on obesity related co-morbidities in patients with obesity and body mass index (BMI) between 30-40 kg/m².

2. INTRODUCTION

[figure not shown]
2.1 Background

The National Institutes of Health, the World Health Organization, and numerous other scientific organizations including the America Medical Association (AMA) recognize obesity as a chronic disease requiring primary therapy. More than one-third of United States adults are obese.¹ The increasing prevalence of obesity in the U.S. has been accompanied by an increasing prevalence in its associated comorbid conditions including hypertension, diabetes, dyslipidemia, coronary heart disease, stroke, sleep apnea, osteoarthritis, gallbladder disease, GERD, nonalcoholic fatty liver disease (NAFLD), and cancer. Obesity is associated with an increased risk of all-cause and cardiovascular mortality and accounts for about 2.5 million preventable deaths annually.²⁻⁴ The economic consequences of obesity are enormous, and projected increases may threaten the integrity of our health care system. Recent analyses estimate that 147 to 210 billion dollars are spent annually to treat obesity-attributable medical problems in the United States, accounting for about 21% of health care expenditures.^{5,6}

Current treatment options for patients with obesity include lifestyle intervention, obesity pharmacotherapy, and bariatric surgery. The components of lifestyle intervention include diet, exercise, and behavior modification and should be considered the cornerstone of any obesity treatment.⁷ However, as a stand-alone therapy, even intensive lifestyle intervention is only modestly effective with an expected percent total body weight loss (%TBWL) < 3%.⁸⁻¹⁰ The available pharmacological approaches for the treatment of obesity increase weight loss by 3% to 9% compared with lifestyle therapy alone, but some can be associated with unfavorable side effects, significant cost, and weight loss achieved by pharmacotherapy is rarely maintained upon withdrawal of the medication.¹¹

The scientific literature is clear in showing that the magnitude of weight loss is strongly associated with improvement in obesity related co-morbidities such as diabetes, blood pressure, hyperlipidemia, obstructive sleep apnea, and fatty liver disease. The odds of clinically significant improvements in obesity related co-morbidities are much higher when %TBWL exceeds 10%.^{12,13} Bariatric surgery, such as Roux-en-Y gastric bypass (RYGB) and sleeve gastrectomy, can achieve significant and durable weight loss that exceeds the 10% TBWL threshold in the majority of patients; however, it is estimated that less than 1% of patients with severe obesity (body mass index [BMI] ≥ 40 kg/m₂) undergo surgical interventions given high costs, patient preference, access to care, and the morbidity and mortality associated with surgery.¹⁴ More importantly, the majority of patients with mild to moderate obesity (BMI 30-40 kg/m₂) who do not qualify for bariatric surgery are left without an effective management approach to their disease, considering the modest effects seen with medications or lifestyle intervention alone and their ability to achieve >10%TBWL only in the minority of patients. Yet, according to the global

Figure 1.

©MAYO
2016

disability-adjusted life-years and deaths study, patients with mild to moderate obesity are the highest contributors to the burden on disease both in terms of co-morbidities and overall mortality¹⁵. Therefore, both government agencies (the Agency for Healthcare Research and Quality [AHRQ]¹⁶) and national societies (American Society of Bariatric and Metabolic Surgery [ASMBs]¹⁷, and American Society of Gastrointestinal Endoscopy [ASGE]¹⁸) now recognize that a significant management gap exists for patients with mild to moderate obesity (BMI between 30-40 kg/m₂) and have defined safety and efficacy thresholds for endoscopic weight loss interventions to achieve societal recommendations. Recently the FDA has approved endoscopic bariatric therapies (EBTs) such as intragastric balloons (IGB) for the management of obesity.¹⁹ These endoscopic therapies can achieve >10%TBWL in the majority of patients with excellent safety and lower cost (roughly one quarter of the cost of bariatric surgery). Furthermore, they are anatomy preserving, reversible, repeatable, and are thus well positioned to fill the gap in the management of obesity.

Endoscopic Sleeve Gastroplasty (ESG) is an endoscopic minimally invasive weight loss procedure where a commercially available, FDA approved, full-thickness endoscopic suturing device (Overstitch; Apollo Endosurgery, Austin, TX) is used to reduce the stomach volume by 80% through the creation of a restrictive endoscopic sleeve (figure 1). This is accomplished by a series of endolumenally placed full-thickness sutures through the gastric wall, extending from the antrum to the gastroesophageal junction.

2.2 Clinical Data to Date

The feasibility of ESG was first demonstrated in humans in the US in 2013.²⁰ Since then, the technique has gained wide clinical adoption in the US and world-wide with more than 2000 cases performed. Multiple single-arm prospective and retrospective studies have demonstrated the safety and minimally invasive nature of the technique and reported %TBWL of about 18% at 12 months.^{21, 22} Furthermore, studies have demonstrated physiologic perturbations resulting from creation of the ESG and its association with increased satiation and metabolic effects that are potentially important to control the metabolic dysregulation associated with obesity.²³ In a recent multicenter study of 248 patients enrolled at Mayo Clinic, Cornell Medical Center, and Madrid Hospital, ESG was associated with 18% and 20% TBWL at 12 and 18 months, respectively²³. More importantly, in this large series, incidence of serious adverse events (SAE) was only 2% and none of these SAEs required any surgical intervention. No mortality was reported.

2.3 Rationale

A joint task force convened by the ASGE and the ASMBs defined safety of efficacy threshold that endoscopic bariatric therapies, such as ESG, need to meet before societies recommend their wide-spread adoption. These thresholds are as follows: EBTs intended as a primary obesity intervention in patients with mild to moderate obesity should achieve a mean minimum threshold of 25% excess weight loss (%EWL) measured at 12 months (calculated based on an ideal BMI of 25mg/kg²). In addition to the absolute threshold of weight loss, the mean %EWL difference between the procedure and control should be a minimum of 15% EWL and be statistically significant. Finally, the risk associated with EBT should equate to a 5%

incidence of serious adverse events or less. Based on this consensus statement, an endoscopic intervention that meets these established thresholds should be considered appropriate to incorporate into wide-spread clinical practice presuming that the appropriate training and credentialing in that EBT has been achieved^{24, 25}.

Despite the excellent clinical experience with ESG, no randomized clinical trials have been performed to evaluate the long-term efficacy of the technique over life-style intervention in producing significant long-term weight loss, improving obesity associated co-morbidities, and meeting the societal thresholds. Furthermore, Level 1 evidence is needed to further advance this promising technique and achieve wide-spread adoption. Therefore, we are proposing a randomized controlled trial to evaluate the long-term safety and efficacy of ESG in meeting efficacy endpoints set forth in a consensus statement by relevant societies (American Society of Gastrointestinal Endoscopy [ASGE] and American Society of Metabolic and Bariatric Surgery [ASMBS]) and its impact on obesity related co-morbidities in patients with obesity and body mass index (BMI) between 30-40 kg/m².

3 STUDY OBJECTIVES

1. Assess if ESG achieves safety and efficacy threshold as defined by joint societal consensus statement by ASGE and ASMBS
2. Assess the impact of ESG on obesity related co-morbidities (Hypertension and Diabetes)
3. Assess the mid-term durability of weight loss achieved by ESG at 24 months.
4. Assess the impact of re-tightening the ESG on weight loss trajectory.

4 STUDY DESIGN

4.1 General Description

This study is a multi-center, randomized, open-label clinical trial evaluating the efficacy and safety of ESG as an adjunct to life-style intervention for weight loss and improvement in obesity-related co-morbidities compared to lifestyle intervention alone in participants with a BMI ≥ 30 and ≤ 40 kg/m² who have failed to achieve and maintain weight loss with a non-surgical program.

Participants will be recruited from outpatient clinical weight loss clinics and from study-related institutional review board (IRB) approved advertisements. The cohort will include nor more than 50 patients without at least one of a) hypertension (HTN) on one or more anti-hypertensive medications or b) type II diabetes mellitus (DM) on oral agents only with HbA1c ≤ 9 . Enrollment will be tracked continuously and enrollment closed to non-DM, non-HTN patients after meeting the target for that group.

Two hundred eligible participants will be stratified into three groups (obesity, obesity-hypertension, and obesity-diabetes) and then block-randomized 1 to 1.5 to treatment (80 participants) and control (120 participants) groups alone as depicted in the diagram on page 16. All treatment group participants will undergo endoscopy and those without endoscopic contraindications will undergo the ESG. All control subjects will follow a low-calorie, healthy lifestyle intervention only for 12 months. After 12 months of lifestyle intervention, eligible control participants will crossover to receive the ESG. Those who had the ESG will undergo a repeat upper endoscopy at 52 weeks +- 4 weeks to evaluate the durability of the plications and re-tighten the ESG if needed with continued follow-up for 12 additional months.

The study will have two levels:

1. Level 1: the randomized study phase with primary outcomes for both groups evaluated at 12 months
2. Level 2: the crossover, non-randomized study phase with outcomes for a) the initial treatment group at 24 months post ESG (12 months after the re-tightening procedure) b) for the controlled cross-over group evaluated at 12 months after ESG

4.2 Endpoints

4.2.1 Effectiveness

Primary:

- % EWL at 12 months from randomization by randomized arm measured at the week 52 visit. The null hypothesis is no difference in mean %EWL between randomized arms.

Secondary:

- Proportion with $\geq 25\%$ EWL at 12 months by randomized arm
- Change in hypertension in the ESG group compared to LS only

- Proportion of patients off or with reduction in their antihypertensive medications in the randomized control arm compared to lifestyle control at 12 months
- Change in systolic and diastolic blood pressure in the randomized arm compared to lifestyle control at 12 months
- Comparing diastolic and systolic blood pressures as continuous variables 12 months after ESG (compared to baseline) in the entire cohort that received ESG both in the randomized and cross-over segments of the trial
- Change in type II diabetes in the ESG groups compared to LS only
 - Proportion of patients off or with reduction in their diabetes medications in the randomized arm compared to lifestyle control at 12 months
 - Change in HgbA1c in the randomized arm compared to lifestyle control at 12 months
 - Comparing HgbA1c as a continues variable 12 months after ESG (compared to before) in the entire cohort that received ESG both in the randomized and cross-over segments of the trial.
- %TBWL in the ESG group compared to LS only
- % of patients in the ESG group achieving > 5% TBWL compared to LS only
- % of patients in the ESG group achieving > 10% TBWL compared to LS only
- Durability of the plication evaluated by endoscopy at 12 months (level 1) and effectiveness of re-tightening procedure performed at 12 months (level 1) in maintaining and / or enhancing weight loss at 24 months. Durability of the plication and procedure is defined as greater than 70% of the cohort undergoing repeat endoscopy achieving a score of ≥ 1 out of 3 prior to re-tightening (Grading system and evaluation in appendix). Efficacy of re-tightening is defined as $\geq 50\%$ of the cohort undergoing the re-tightening maintaining or losing weight compared to the re-tightening weight at 12 months after the re-tightening procedure.
- Incidence of esophagitis at repeat endoscopy at 12 months (level 1). (LA grading system in form in appendix)
- Changes in quality of life assessed using standard validated questionnaires (IWQOL-lite and SF-36)
- Changes in depression assessed using PHQ-9 questionnaire
- Improvement/reduction of hunger and desire to eat evaluated using validated self-reported ratings of appetite based on a 100-mm visual-analogue scale
- Improvement in eating behaviors evaluated using the Three Factor Eating Questionnaire (TFEQ)
- Among LS randomized group with ESG at 12 months – outcome of 24 month %EWL

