5.3 Screening and Eligibility Assessment

Screening will be conducted by the investigator or the co-investigator and documented on the Investigator delegated/medically qualified team member intake form (conventionally known as PI Intake Form) (Appendix A) and Screening Labs form (Appendix B). Screening must occur no more than 45 days prior to randomization.

Screening will include the following:

1. Sign informed consent form
2. Screening exam and intake by the investigator or co-investigator
3. Height, weight and BMI; waist and hip circumference; vital signs (blood pressure and pulse)
4. Dietary screening intake and approval
5. Laboratory tests (after 8 hours fasting)

- **CBC:** Hgb, Hct, WBC, MCV, platelets
- **Chemistry panel:** sodium, potassium, chloride, CO₂, BUN, creatinine, fasting glucose, insulin, SGOT/AST, SGPT/ALT, alkaline phosphatase, total bilirubin, direct bilirubin, total protein, albumin, fasting lipids profile (total cholesterol, triglyceride, LDL cholesterol, HDL cholesterol) Fe/TIBC, iron, B12, 25-Hydroxy Vitamin D, TSH, total Ghrelin level (only if available at participating institution), C-reactive protein.
- **Coag:** Pro Time or INR, PTT
- **PYY-1, GLP-1, Total Ghrelin** pending sites' availability to analyze
- **Urinalysis**
- **HgbA1C**
- **H. Pylori Breath Test.** **Patients with a positive h-pylori breath test will be treated and eradication must be confirmed with a stool antigen after treatment and prior to randomization**
- **EKG** for patients 50 years old or older
- **Urine pregnancy test** for women of child bearing potential

6. Questionnaires
7. Psychological evaluation and approval: Study psychologists will use their standard clinical evaluations for bariatric interventions.

Within one week of completion of the screening tests, the PI will review the results and determine the participant's eligibility. The center will inform the participant of their screening results within 10 days of completing testing. Any abnormal lab results will be communicated to the participant and they will be required to notify their primary care provider for any further action that may be necessary. All potential participants who qualify for randomization based on the initial screening assessments will return for a randomization visit where participants will have the chance to review any questions with the study staff, as well as a recap of the follow-up schedule, and they will then receive their randomization assignment.

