	Enrollment; Screening/ Baseline	Randomization / Week 1 visit	Weeks 4, 8	Week 12	Weeks 16, 20	Week 24 (6 month)	Weeks 30, 36, 42, 48	Week 52 (Final Year 1 visit), re-screen for crossover to ESG	Unscheduled Visit
Visit Number	-1	1	2,3	4	5,6	7	8,9,10,11,	12	
Informed consent	X								
Complete Physical Exam (CPE) by Investigator or Investigator delegated / medically qualified team member	X			X		X	X	X	X
Investigator or Investigator delegated/medically qualified team member exam		X ⁺⁺	X	X	X	X	X	X	X
EKG if (> 50 yo)	X							X	
Formal nutritional assessment	X								
Formal psychology evaluation	X								
Pregnancy test (females of childbearing potential only)	X								
Laboratory tests, H-pylori breath testing (baseline only)* *	X							X	
Questionnaires#	X			X		X		X	
Inclusion/exclusion criteria	X							X	
Endoscopy / Procedure									
Procedure Assessment Form									
GERD Questionnaire + Activity Assessment Form	X	X	X	X	X	X	X	X	
Weight, BMI/height, Waist and Hip Circumference Form	X	X	X	X	X	X	X	X	X
Vital Signs Form	X	X	X	X	X	X	X	X	X
Adverse Events Form		X	X	X	X	X	X	X	X
Medications Form##	X	X	X	X	X	X	X	X	X
Post-enrollment Nutrition / Exercise / satiety counseling and assessment		X	X	X	X	X	X	X	
Randomization to ESG vs. LS ⁺		X							
Subject Satisfaction Questionnaire (control phase)								X	

** Electrolytes, Creatinine, CBC, Iron, TIBC, B12, 25-hydroxy Vitamin D, TSH, HgA1c, fasting blood sugar and insulin, PTT, fasting lipids profile (total cholesterol, LDL, HDL, and Triglyceride), ALT, AST, ALK-P, total bilirubin, direct bilirubin, BUN, total protein, albumin, CRP, urinalysis; also include PYY-1, GLP-1 and total Ghrelin pending sites' availability to analyze

Eating disorder questionnaire + hospital anxiety and depression questionnaires (only at base-line), IWFQOL-Lite, SF36, PHQ9, Pittsburgh Sleep Quality Index (PSQI), Three factor eating questionnaire (TFEQ)

Record all medications including dose and frequency; especially diabetes and blood pressure medication.

+ LS start with the week 1 visit with no transitional diet.

++ Required only for Week 1 visit

5.6.1.1.4 Schedule of Events for Control Group, Crossover in Year 2, Level 2

[figure not shown]
TABLE 3. MERIT SCHEDULE OF EVENTS (Year 2, Level 2, Control Group, cross-over 120 patients)									
	ESG Procedure	Post-Op Phone Call	Weeks 1, 4, 8	Week 12	Weeks 16, 20	Week 24 (6 month)	Weeks 30, 36, 42, 48	Week 52 (Final Year 1 visit)	Unscheduled Visit
Visit Number	0	-	1,2,3	4	5,6	7	8,9,10,11	12	

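### The reference visit for the pooled blood-pressure endpoint is not fixed for crossover patients: read by the schedule's own labels, it would add the lifestyle year to their ESG change

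*Combined protocol and SAP*

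**What the plan says.** Section 4.2.1 lists two pooled before-and-after comparisons among the secondary endpoints, one for blood pressure and one for HbA1c. Both cover everyone who receives ESG, at randomization or after crossover, but their reference points are worded differently:

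- Blood pressure: "12 months after ESG (compared to baseline) in the entire cohort that received ESG both in the randomized and cross-over segments of the trial".
- HbA1c: "12 months after ESG (compared to before) in the entire cohort that received ESG both in the randomized and cross-over segments of the trial".

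In the Section 5.6 schedules, the only column that carries the word baseline is "Enrollment; Screening/ Baseline". The control Year 1 table also restricts H. pylori testing to baseline, and its mark for that test is in this column. The crossover Year 2 table has no baseline column and begins with the ESG procedure as visit 0, although its footnote still limits some questionnaires to baseline.

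Later pre-ESG readings are scheduled for crossover patients. The row "Vital Signs Form", which by Section 5.3 includes blood pressure, is marked at the control visit "Week 52 (Final Year 1 visit), re-screen for crossover to ESG" and again on the crossover procedure day. Laboratory tests, including HbA1c, are also marked at that Week 52 visit.

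Section 7.2.2 gives a between-arm ANCOVA for blood pressure and HbA1c. It names neither a method nor a reference visit for the pooled comparisons. For weight in the control arm, it measures the second-year change from the 12-month assessment.

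**The concern.** A programmer who takes baseline from the schedule labels will pick enrolment. For a patient randomized to ESG, that visit is shortly before the procedure. For a crossover patient, it precedes a full year of lifestyle intervention. One pooled mean would then combine two intervals and two treatment histories and be reported as the change 12 months after ESG.

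The effect of ESG on hypertension and diabetes is the second study objective (Section 3), and the pooled comparison is the largest ESG data set for it. Leaving the reference open in an open-label trial also allows a choice among three candidate readings (enrolment, Week 52, procedure day) after the data are seen. In addition, the blood-pressure and HbA1c results could rest on different reference visits in the same patients.

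**Working it through.** **Inputs.** ESG arm 80 and lifestyle arm 120; up to 20% of controls succeed on lifestyle alone and up to 20% are lost before 12 months; 70 completers assumed for the Level 2 power (all Section 7.1). Screening is at most 45 days before randomization (Section 5.3). ESG follows within 30 days of randomization (Section 5.4). The lifestyle period is 12 months (Section 4.1).

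**Plan's own figure.** Expected crossovers: 120 × 0.8 × 0.8 = 76.8, which rounds to the 77 stated in Section 7.1. It reproduces.

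**Crossover share of the pooled cohort.**
- 77/(80 + 77) = 77/157 = 49.0%
- 70/(80 + 70) = 70/150 = 46.7%

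**Interval covered if the reference is enrolment.**
- Randomized to ESG: enrolment to ESG is at most 45 + 30 = 75 days, or about 2.5 months. To 12 months after ESG, this is about 12 to 14.5 months.
- Crossover: enrolment to the Week 52 re-screen is 52 to 52 + 45/7 = 58.4 weeks. Adding 52 weeks after ESG gives 104 to 110.4 weeks, about 24 to 25 months, plus any wait between re-screen and procedure.

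**Effect on the pooled mean.** Let w be the crossover share, L the mean blood-pressure change in crossover patients from enrolment to their pre-ESG reading, and X and R the mean changes after ESG in crossover and randomized patients.
- Enrolment as reference: w(L + X) + (1 − w)R
- Pre-ESG reading as reference: wX + (1 − w)R
- Difference: wL

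The documents give no value for L. The values below are assumptions that show the scale in both directions (systolic, mmHg):

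| Assumed L | Shift, w = 49.0% | Shift, w = 46.7% |
|---|---|---|
| −5 | −2.45 | −2.33 |
| −3 | −1.47 | −1.40 |
| −1 | −0.49 | −0.47 |
| 0 | 0 | 0 |
| +1 | +0.49 | +0.47 |
| +3 | +1.47 | +1.40 |

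A fall during the lifestyle year flatters ESG; a rise counts against it. With a pre-ESG reference the shift is zero by construction.

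**Reference points for crossover patients, side by side.**

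| Measure | Reference wording | Natural reading |
|---|---|---|
| Blood pressure (4.2.1) | baseline | enrolment, by schedule label |
| HbA1c (4.2.1) | before (ESG) | Week 52 laboratory tests |
| Weight (7.2.2) | 12-month assessment | Week 52 visit |

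For HbA1c, the control Year 1 table marks laboratory tests only at enrolment and Week 52, and the crossover table only at Weeks 24 and 52 after ESG. The control Week 52 visit is therefore the only scheduled HbA1c after the lifestyle year and before ESG.

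**The case against.** The strongest reply is that nothing in the plan forces the enrolment reading. The endpoint is timed from ESG, its HbA1c twin says before, the crossover weight analysis restarts at 12 months, and blood pressure is scheduled both at the Week 52 re-screen and on the procedure day. Read together, these favour a pre-ESG reference. This stands, and it limits the point to an inconsistency with a conditional consequence. It does not remove the point: the word actually used for blood pressure is the one the schedules reserve for enrolment, and no later section overrides it.

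A reader might infer that the plan credits a year of lifestyle benefit to ESG and so overstates the effect by a known amount. The documents do not support that. They give no blood-pressure change for the lifestyle year, and its direction is unknown because medication changes could move pressure either way. Crossover is also aimed largely at controls who lost less weight: Section 7.1 removes those reaching 25% EWL before counting crossovers. The change in this subgroup may therefore be smaller than in all controls.

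A reader might also expect regression to the mean to produce a false fall. No criterion selects patients for a high reading. Hypertensive patients enter by being on medication (Sections 4.1 and 4.5), and Section 4.6 excludes poorly controlled hypertension.

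Finally, the endpoint is secondary and non-randomized. That is correct and bears on its weight.

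**Conclusion.** The point holds as an inconsistency in the reference visit. If enrolment is used, 47% to 49% of any lifestyle-year blood-pressure change in crossover patients, in either direction, passes into the pooled figure reported for ESG. If a pre-ESG value is used, none does.

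The share rests on the plan's expected counts: 77 crossovers or 70 completers, with all 80 patients in the ESG arm contributing. It also assumes that every patient carries equal weight. The size in mmHg cannot be stated from the documents, and the table above shows scale only. It is worth correcting before analysis. It does not touch the primary %EWL analysis or the randomized blood-pressure comparison at 12 months.

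**What to change.** In Section 4.2.1, replace the two reference words in the pooled blood-pressure and HbA1c endpoints with one definition, and repeat it in Section 7.2.2: the last scheduled clinic measurement before the patient's own ESG. State that this is the screening visit for patients randomized to ESG and the Week 52 re-screen visit for crossover patients.

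Say explicitly that procedure-day vital signs are not the reference. No laboratory tests are scheduled that day, so HbA1c could not share the visit. Section 5.5 also starts IV hydration before the procedure, and the schedule does not say whether the reading comes first.

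Report the randomized and crossover segments beside the pooled figure, so that a difference between them is visible.

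The cost is a sentence in each of two sections and two extra rows in a results table. The vital signs and laboratory tests needed are already scheduled, so no new data are collected.
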